#### 4.1.2 Secondary Study Endpoints

The following parameters will be measured or evaluated in each leg for independent analysis of each limb

1. Change in ankle dorsiflexion strength
2. Change in ankle plantarflexion strength
3. Change in ankle inversion strength
4. Change in ankle eversion strength
5. Change in ability to perform activities of daily living
6. Subject frustration with injury
7. Subject perception of recovery from injury
8. Pain in the 24 hours following running
9. Change in running duration including weekly and longest run
10. Change in running speed
11. Subject confidence in increasing the duration and intensity of running

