## 3 Study Objectives and Purpose

- Primary Objective: To assess the efficacy of OnabotulinumtoxinA (Botox) on decreasing pain associated with R-CECS.
- Secondary Objective: To assess the safety and tolerability of Botox injections of Botox for patients with R-CECS
- Secondary Objective: To assess the ability to return to sport following injection of Botox in subjects with R-CECS

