#### 8.2 Statistical Methods

Basic descriptive statistics, means (SD) and medians (IQR) for continuous variables and frequencies (percentages) for categorical variables will be used to summarize patient outcomes. For the primary outcome, change in pain (from baseline on 0-10 numeric rating scale) will be assessed at each time point (2,4,6 months) using Friedman's ANOVA. Friedman's ANOVA is the non-parametric analog to one-way repeated measures ANOVA and is often

used for ordinal outcomes. If necessary and feasible, GEE models will be constructed to further assess changes in pain while accounting for intra-subject correlation. Secondary endpoints utilizing the UWRI will also be assessed in this manner. Change in strength outcomes at baseline and 2 months will be assessed using Wilcoxon signed rank tests or, if necessary, linear mixed effects models for repeated measures, to account for intra-subject correlation (left and right legs).

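### Section 4.1.2 puts a per-leg rule over six secondary endpoints that describe the subject (items 5-7 and 9-11), and section 8.2 does not name the unit, so one answer can be analysed as two.

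*Combined protocol and SAP*

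**What the plan says.** Section 4.1.2 opens its list of 11 secondary endpoints with "The following parameters will be measured or evaluated in each leg for independent analysis of each limb" and exempts none of them. Items 1-4 are ankle strength in four directions. The rest include "Change in ability to perform activities of daily living" (item 5), "Subject frustration with injury" (6), "Subject perception of recovery from injury" (7), "Pain in the 24 hours following running" (8) and "Change in running duration including weekly and longest run" (9), followed by running speed (10) and confidence in increasing running (11).

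Section 8.2 assigns Friedman's ANOVA to the primary pain outcome, with GEE as a conditional further step, and then says "Secondary endpoints utilizing the UWRI will also be assessed in this manner". It does not name the Friedman block. Left-right correlation is mentioned explicitly only for strength, and there too the model that handles it is conditional.

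Section 4.1, Table 3 and Table 4 schedule the UWRI at each contact (baseline, 2, 4 and 6 months) and mention no per-leg version. The Study Summary counts 10 subjects as 20 legs, and section 8.1 plans on independent leg scores. Section 3 lists as a secondary objective "To assess the ability to return to sport following injection of Botox in subjects with R-CECS", and section 2.1 names the UWRI as the instrument for return to sport.

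**The concern.** The per-leg rule cannot be applied to some of the endpoints it covers. A subject has one weekly running duration, one longest run and one running speed. The other four items could in principle be asked about each leg, but the plan describes no form that does so. Someone who follows section 4.1.2 literally must either copy one answer to both legs or invent a second administration of the questionnaire.

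If answers are copied and the legs pooled, 10 independent observations become 20 records. The mean change is unaffected when every subject is duplicated, but its apparent precision is not: tests reject too often and standard errors are too small. The items affected carry the return-to-sport objective. Section 8.1 says that the pilot exists to supply preliminary effect sizes for later power calculations, so false precision here could pass into those plans.

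**Working it through.** **Inputs.** 10 subjects and 20 legs (Study Summary, section 8.1). Contacts at baseline, 2, 4 and 6 months (Table 3). Friedman's ANOVA (section 8.2). The documents give no alpha, so 0.05 is assumed. The number of time levels is taken as three (change at 2, 4 and 6 months) or four (baseline included), because section 8.2 can be read either way. The documents do not map endpoints to UWRI questions. Items 5-11 are taken as the UWRI endpoints because strength is the only secondary group given a separate method.

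**The plan's own figure.** Section 8.1 claims 80% power with 6 patients for a 2-point fall, SD 1. Take four time points with means 0, -2/3, -4/3 and -2. The squared deviations from their mean sum to 1 + 1/9 + 1/9 + 1 = 2.222, so the noncentrality is 6 × 2.222 = 13.33 on 3 and 20 degrees of freedom, and power is 0.802. The figure is reproduced with 6 observations per time point; 12 independent legs would give 0.992. This calculation concerns pain and is not altered by the present point.

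**Which items have a value per leg.**
- Items 1-4 (strength): yes.
- Item 8 (pain after running): possible, since the primary pain endpoint in section 4.1.1 is scored in each leg.
- Items 9 and 10 (running duration, running speed): no.
- Items 5, 6, 7 and 11: worded about the subject, with no per-leg form described.

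Six items are therefore affected: 5, 6, 7, 9, 10 and 11.

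**Effect of copying on Friedman's statistic.** With b blocks, k time levels and rank sums R_j,

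Q = 12/(b·k·(k+1)) · ΣR_j² − 3·b·(k+1).

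Copying every block replaces b by 2b and R_j by 2R_j. The first term becomes 4/2 = 2 times its value and the second also doubles, so Q doubles exactly. A test at nominal 5% then rejects whenever the correct Q exceeds half the critical value:
- k = 3: P(χ²₂ > 5.99/2) = 22.4%
- k = 4: P(χ²₃ > 7.81/2) = 27.2%

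**Simulation, no true change, 10 subjects.** Ranges cover continuous and tied ordinal scores across separate simulations.

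| Records entered | 3 levels | 4 levels |
|---|---|---|
| One per subject | about 5% | about 4.5% |
| All 10 subjects duplicated | 22-23% | 27-29% |
| 5 of 10 duplicated | 16-17% | 19-20% |
| 3 of 10 duplicated | 13-14% | about 15% |

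**Standard error.** With the SD held fixed, the naive standard error goes from SD/√10 to SD/√20, too small by √2 = 1.41. A t-based interval has (2.093/√20)/(2.262/√10) = 0.65 of its proper width.

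**Effect on a subject-clustered GEE.** With an independence working correlation and robust errors, copying every row leaves the estimate unchanged. Each outer (bread) factor of the sandwich variance is halved, and the middle, a sum of squared subject scores, is multiplied by 4. The net factor is ½ × 4 × ½ = 1. A numerical check on 10 subjects and four visits gave identical estimates and standard errors before and after copying.

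**The case against.** The strongest reply is that the plan does not say that 20 records will be pooled. Independent analysis of each limb could mean that left and right are analysed separately. Each analysis would then hold at most 10 records, with no doubling. Section 8.2 also names a GEE that accounts for within-subject correlation, and section 8.3 names GEE or linear models for incomplete data. In addition, section 5.2 does not require bilateral disease, so 20 legs may not be reached.

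Much of this stands. Double counting is permitted by the text, not certain, and the error rates above are upper bounds. A reader might infer that no correlation model could repair a copied answer. That is wrong: the subject-clustered GEE cancels exact duplication. However, section 8.2 makes that GEE conditional and words it for pain, and 10 clusters are few for robust standard errors. The left-right reading avoids inflation, but for a copied answer it would report the same analysis twice, so it does not make the rule workable either.

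A reader might also count seven affected endpoints by including item 8. The documents do not support that, because pain can be scored in each leg. Nor do they settle that items 5-7 and 11 could never be asked per leg: the UWRI form is not in the documents, and only items 9 and 10 are impossible to split.

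**Conclusion.** The point holds for six secondary endpoints: with certainty for running duration and speed, and for the other four because no per-leg form is described. The stated rule cannot be followed for these items without duplicating an answer or adding an undescribed procedure, and the analysis section does not name the unit that would prevent double counting.

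The 22% (three levels) and 27-29% (four levels) rejection rates, against about 4.5-5% when done correctly, rest on four assumptions: all 10 subjects bilateral, identical answers entered for both legs, legs pooled, and Friedman's test alone. With half the subjects bilateral the rates are roughly 16-17% and 19-20%. They should not be read as the expected error rate of this trial.

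Nor does the point invalidate the sample size or the primary pain analysis, as a reader might infer: the items are secondary, the study is an open-label pilot, and the power statement concerns pain. It is a correction that should be made before the data are analysed.

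**What to change.** In section 4.1.2, limit the per-leg rule to items 1-4, and to item 8 if it is collected per leg; state which applies to item 8. Add that items 5-7 and 9-11 are recorded once per subject at each contact and analysed with the subject as the unit (n=10).

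In section 8.2, state that these six endpoints enter as one record per subject per visit, with the subject as the Friedman block.

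The cost is a few sentences of protocol text. Stated precision for these items becomes less favourable than a 20-leg analysis would show. No new data are needed and the sample size is unchanged.

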#### Long-range risks

- TA weakness resulting in foot drop
- Lateral compartment weakness resulting in eversion weakness
- Plantarflexion weakness resulting in weakness with plantarflexion
- Distant spread resulting in botulism-like symptoms including muscle weakness all over body, vision problems, difficulty speaking or swallowing, trouble breathing, loss of bladder control, respiratory compromise, death (see black box warning of Botox labelling)

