#### 4.1.3 Primary Safety Endpoints

1. Lower extremity weakness
2. Bruising, bleeding, pain, redness, or swelling where the injection was given

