### **6.4 Route of Administration**

- Dose will be determined based upon patient location of symptoms as follows:
  - - 50 units total (25 proximal and 25 distal) into the TA for anterior symptoms
  - - 50 units in to the peroneal longus for the lateral compartment
  - - 50 units into each the medial and lateral gastrocnemius for superficial posterior symptoms
  - - 50 units into the tibialis posterior for deep posterior symptoms
- Treatment duration: Established duration of action on muscular weakness of other uses of Botox is between 2 and 4 months. Given this novel treatment, duration of action in our study is unknown.
- Expected side effects include:
  - Weakness in the muscle injected
  - Injection site pain
  - Injection site bleeding

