## 7.2 Established Standard of Care:

**Table 3.** Study Calendar

Process	Screening	Baseline (initial clinic visit; time 0)	Follow-up 1 (2 months, in clinic)	Follow-up 2 (4 months, telephone)	Final Visit (6 months, telephone)
IMP Measurement	SOC	X			
UWRI		X	X	X	X
Kio Force Measurement		X	X		
Botox injection into TA		X			

Indicate if study or standard of care by using "X" for study and "SOC" for standard of care.

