### **8.3 Subject Population(s) for Analysis**

The subject population for analyses will include all patients who receive the Botox injection. We intend to minimize loss to follow-up; however, if patients drop out of the study, we will attempt to use statistical methods that allow for missing outcomes (e.g. GEE/Linear models for repeated data) so that all available data can be used for analysis.

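### Ankle strength is analysed in every leg without regard to which muscle was injected, so the estimated loss in each direction is attenuated and depends on case mix

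*Combined protocol and SAP*

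**What the plan says.** Treatment differs between patients. Section 6.4 states: "Dose will be determined based upon patient location of symptoms as follows". It then lists tibialis anterior (TA), peroneal longus, both heads of gastrocnemius, and tibialis posterior, each for its own compartment. Section 2.6 gives the same list.

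Section 2.7.1 links muscle groups to their own losses: "TA weakness resulting in foot drop" and "Lateral compartment weakness resulting in eversion weakness", plus a plantarflexion entry. It has no entry for inversion.

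The strength endpoints in 4.1.2 are change in dorsiflexion, plantarflexion, inversion and eversion, introduced by "The following parameters will be measured or evaluated in each leg for independent analysis of each limb". On the analysis, 8.2 says: "Change in strength outcomes at baseline and 2 months will be assessed using Wilcoxon signed rank tests". The alternative is a mixed model, if needed, whose stated purpose is to handle correlation between left and right legs. Section 8.3 adds: "The subject population for analyses will include all patients who receive the Botox injection".

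The first primary safety endpoint in 4.1.3 is "Lower extremity weakness", which 10.1 says will be both quantitative and qualitative. The study calendar (Table 3, section 7.2) has only the row "Botox injection into TA", which does not agree with the symptom-based list in 2.6 and 6.4.

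**The concern.** A leg injected only in peroneal longus has no direct reason to lose dorsiflexion strength. Under 4.1.2, 8.2 and 8.3 nothing keeps it out of the dorsiflexion analysis or marks it as uninjected for that direction. The pooled mean then mixes injected and uninjected muscles. It estimates a quantity that changes with the mix of compartments among ten patients, not the effect of the injection on the muscle that received it.

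Two stated aims are affected. Section 2.1 presents force-sensor measurement as an improvement on manual muscle testing. Section 8.1 says the pilot should supply effect sizes for later studies. An attenuated strength effect carried into a later study with a different case mix would mislead its planning. The attenuation also runs towards understating weakness, which is the quantity of interest for safety.

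**Working it through.** **The plan's own figure.** Section 8.1 gives a sample size for pain only: 80% power with 6 patients, raised to 10 patients (20 legs). A one-way ANOVA with four time points, an assumed linear fall from 0 to 2 points, SD 1 and alpha 0.05 gives power 0.802 with 6 units per time point. Then 6/0.85 = 7.06. Dividing by a Friedman efficiency of 0.955 × 4/5 = 0.764 gives 9.24, hence 10. The figure can be reproduced on that reading, and the present point does not touch it. The plan states no figure for strength.

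**Inputs**
- Legs: 20 (8.1), treated here as independent. Correlation between a patient's two legs would reduce the information.
- Test: Wilcoxon signed rank (8.2). Alpha is not stated; two-sided 0.05 is assumed.
- f, the share of legs injected in the muscle that drives a given direction: not stated. Section 2.1 says only that CECS is mostly anterior. Range shown: 25% to 90%.
- d, the true standardised loss in an injected muscle: not stated. Assumed 1 SD of the change, with no loss in uninjected muscles.

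**Attenuation.** Pooled mean loss = f × d + (1 − f) × 0 = f × d. With d = 1 SD, the pooled mean is 0.90, 0.75, 0.50 and 0.25 SD at f = 90%, 75%, 50% and 25%. In the injected legs alone it stays at 1 SD. This step needs no assumption about power.

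**Power by simulation.** Changes are normal with SD 1, shifted by d in the injected legs only:

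| Share injected | Injected legs | Power, all 20 legs | Power, injected legs only |
|---|---|---|---|
| 90% | 18 | 96% | 97% |
| 75% | 15 | 83% | 93% |
| 50% | 10 | 44% | 79% |
| 25% | 5 | 12% | 0% |

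Repeat runs agree within about a percentage point or two.

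**The last row.** With 5 legs the most extreme signed rank result has two-sided p = 2 × (1/2)^5 = 2/32 = 0.0625, so the test can never reject at 0.05. With 6 legs the minimum is 2/64 = 0.031.

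**Sensitivity to d at f = 50%.** All legs against injected legs: 33% against 60% for d = 0.8, and 71% against 98% for d = 1.5. The ordering does not depend on d = 1.

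**The case against.** **The plan is silent rather than explicit.** Section 8.2 does not say that legs are pooled whichever muscle was injected, and 8.3 defines a set of patients, not a set of legs for each direction. That is fair. But 4.1.2 asks for every direction in each leg, and nothing in the plan separates legs by injected muscle. A statistician following the text would pool.

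**The share may be high where it matters most.** CECS is mostly anterior (2.1), and compartments may be combined: the earlier study described in 2.1 injected anterior and anterior/lateral compartments. If 90% of legs receive a TA injection, dorsiflexion is barely diluted. This stands, and a reader should not infer that dorsiflexion is badly affected. A mostly anterior case mix would, however, leave the other directions diluted more.

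**A reader might infer that the plan hides weakness and makes the drug look safe.** The documents do not support that. Section 10.1 makes weakness qualitative as well as quantitative, Table 4 schedules side-effect checks at 2, 4 and 6 months, and 10.3 records adverse events for each patient. Foot drop in one leg would be recorded whatever the group mean shows.

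**A reader might also infer that restricting the legs always gains power.** It does not. A t-test would give about 40% power in five injected legs, but 8.2 names the Wilcoxon test, which has none there. In small subsets the gain is an undiluted estimate, not a test.

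**The mapping is incomplete and power is a weak yardstick.** Section 2.7.1 ties no injected muscle to inversion, and the assumption of no loss elsewhere is not sourced. Strength change is a secondary endpoint in a small pilot. Both points stand. The case therefore rests on the attenuated estimate, with power only as illustration.

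**Conclusion.** The point holds for the quantitative strength estimates. As the plan reads, each direction's pooled mean change is f × d, so it is attenuated by the share of legs injected in the matching muscle and varies with case mix. The reported loss is 90% of the true one at f = 90% and 25% at f = 25%. Under the planned test, separating the legs makes almost no difference to power at 90% injected, a clear difference at 50% (44% against 79%), and leaves no usable test at 25%.

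These sizes rest on an assumed 1-SD loss, none in uninjected muscles, independent legs and alpha 0.05. The documents fix neither the share nor the expected loss. The capture of individual weakness events, the pain endpoint and the sample size are not affected. The plan should be changed on this point, but it is not a flaw in the primary analysis.

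**What to change.** In 4.1.2 and 8.2:

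1. For each direction, make the main strength estimate the change from baseline to 2 months in legs whose injected muscle acts in that direction. Take the injected muscles from the procedure note, already a source document under 9.2.1.
2. Have the investigators fix the muscle-to-direction mapping, including inversion, before analysis.
3. Report the remaining legs separately, or add an injected-muscle term to the mixed model that 8.2 already foresees. Keep the all-leg summary as supportive.
4. Where five or fewer legs qualify, give the estimate with an interval and the individual changes in place of a Wilcoxon test.
5. Reconcile the Table 3 row "Botox injection into TA" with 2.6 and 6.4, since the share of injected legs in every direction depends on it.

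The cost is one derived variable and a few sentences of text, with no new visit or measurement. The downside is fewer legs per direction, wider intervals, and no usable Wilcoxon test in the smallest subsets.

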#### 4.1.3 Primary Safety Endpoints

1. Lower extremity weakness
2. Bruising, bleeding, pain, redness, or swelling where the injection was given

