## 4 Study Design and Endpoints

### 4.1 General Design

- Design: Pilot study without randomization or blinding
- Please see page 6 for schematic design of trial including duration of subject participation
- Summary: Subjects will be enrolled in study at initial clinic visit by study staff at which time diagnosis of R-CECS will be established based on elevated pressure measurements in patients who have had surgical release of the affected compartments. Pressure testing will be performed outside of the clinical study and will be required to establish the diagnosis of R-CECS.

Initial clinic visit with study staff will consist of baseline measurements of ankle plantarflexion, dorsiflexion, inversion, and eversion strength using Kiio Force Sensor. The clinic visit with study staff will establish time point 0 and will consist of written consent for participation, Botox injection, and baseline UWRI. Two months following this visit, the patient will have follow up with study staff. Study staff will again measure ankle strength (ankle inversion, eversion, plantarflexion, and dorsiflexion) using the Kiio Force Sensor utilizing the same strength assessment protocol. Study staff will monitor for side effects and administer the UWRI. Telephone follow up assessment of the UWRI will be made by study staff at 4 and 6 months. For patient incentive, money will be distributed in person consisting of: \$100 at time of injection, \$50 at 2 month follow up, and \$50 following the 6 month follow up. The final payment will be mailed to the subject to an address they provide at the time of follow up.

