### **6.6 Dose Adjustments/Modifications/Delays**

Following injection, dosage cannot be changed and study will maintain the aforementioned dose for the duration of this study. Based on studies for other indications, Botox has been shown to take effect in approximately 2 weeks and last between 2 and 4 months.

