### 7.4.2 Follow up:

**Table 4.** Acceptable Window for Study Visits (including weekends)

Visit	Window	Activities
-------	--------	------------

Study visit 1 (establishes time 0 of study)	Within 1 months of IMP measurement	
 
Written consent reviewed and collected
 
UWRI baseline
 
Kiio Force measurement
 
Botox injection
 

Follow-up 1 (Clinic)	2 months +/- 5 days	
 
UWRI
 
Kiio Force measurement of
 
Evaluation for side effects
 

Follow-up 2 (Telephone)	4 months +/- 1 week	
 
UWRI
 
Evaluation for side effects
 

Follow-up 3 (Telephone)	6 months +/- 1 week	
 
UWRI
 
Evaluation for side effects
 

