## 10 Assessment of Safety

### 10.1 Specifications of Safety Parameters

Lower extremity weakness will be both quantitative and qualitative data.

Bruising, bleeding, pain, redness, or swelling where the injection was given will be qualitative data

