## 11 Study Monitoring, Auditing, and Inspecting

### 11.1 Medical Monitoring

The Principal Investigator will serve as the medical monitor for the study. In the design of the study, the investigators will have regular follow up with the research participants to allow close monitoring for AE/SAEs. Should AE/SAEs occur outside of clinical hours, participants will be provided at time of consent with appropriate instructions for contacting clinician for triage.

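### Between discharge on injection day and the 2-month visit no safety enquiry is scheduled, so site reactions that appear and resolve after discharge, and early or brief weakness, depend on the subject calling or on recall and may be under-counted

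*Combined protocol and SAP*

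**What the plan says.** Safety and tolerability is a secondary objective in section 3. Section 4.1.3 lists two primary safety endpoints: "Lower extremity weakness", and "Bruising, bleeding, pain, redness, or swelling where the injection was given". Section 10.1 adds that "Lower extremity weakness will be both quantitative and qualitative data", while site reactions are to be qualitative only.

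**Before discharge.** Section 7 has the sites watched after injection until bleeding stops, and for reactions that show at once. Section 11.1.1 repeats that subjects are monitored straight after the procedure. Table 4 does not list side-effect evaluation among the visit 1 activities, and Table 3 has no side-effect row.

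**First scheduled contact afterwards.** Section 4.1 states: "Two months following this visit, the patient will have follow up with study staff". Table 4 sets the window at "2 months +/- 5 days" and lists side-effect evaluation there and at 4 and 6 months. Force-sensor strength is measured at baseline and 2 months only.

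**In between.** Subjects receive instructions for reaching a physician (sections 2.7.2, 2.7.4 and 11.1). Section 2.7.2 promises follow-up before 2 months if weakness occurs, and section 7.4.3 starts once the investigators hear of an event. Section 10.3 requires the investigator to ask at each visit about events since the previous one, and to record onset, severity, changes in severity and resolution.

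**Drug effect.** Section 6.6 says "Botox has been shown to take effect in approximately 2 weeks and last between 2 and 4 months". Section 6.4 also gives 2 to 4 months, section 2.6 gives 2 to 6 months, and the Study Summary gives a typical 10 to 12 weeks.

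**The concern.** Section 2.7.1 classes injection-site pain, infection, bleeding and swelling as immediate risks, and the drug effect is said to begin at about 2 weeks. The schedule goes from the day of injection to about 2 months later. A reaction that develops at home and clears within days or weeks falls wholly inside that gap, as does weakness that begins and ends within it.

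The use is unapproved (section 2.3), the protocol knows of no published data in R-CECS (sections 2.1 and 2.5), and the pilot is meant to prepare further studies (section 8.1). With 10 subjects, each one missed moves a subject-level rate by 10 percentage points. The gap also delays the team's awareness of early weakness or of the distant-spread symptoms in section 2.7.1. There is little backstop: the principal investigator acts as data monitoring committee, medical monitor and study monitor, and independent audits are ruled out (sections 10.6, 11.1 and 11.1.1).

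**Working it through.** The plan states no figure on this point, so there is none to reproduce. The check sets the schedule against the stated time course.

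1. **When the first scheduled enquiry falls.** Taking a month as 30.4 days, 2 × 30.4 = 60.8. The window is 60.8 − 5 = 55.8 to 60.8 + 5 = 65.8, or about day 56 to 66. Counted from the stated onset at about day 14, that is 56 − 14 = 42 to 66 − 14 = 52 days later.

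2. **What the pre-discharge check covers.** It can see bleeding, pain or swelling present before the subject leaves. It cannot see bruising, redness, swelling or infection that appears later, or weakness that starts at about 2 weeks. Section 10.3 would require an event noticed before discharge to be recorded. With no entry in Table 4 and no described form for the check, the records may not distinguish ‘looked for and absent’ from ‘not recorded’.

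3. **What covers the gap.** There are two routes. One is contact started by the subject (sections 2.7.2, 2.7.4, 7.4.3 and 11.1). The other is the section 10.3 question at the 2-month visit, which asks the subject to look back over about 56 to 66 days. That question is prompted, but onset, resolution and changes in severity of a short event must then come from memory.

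4. **Where the force-sensor reading falls against the stated durations.**
   - 10 to 12 weeks: 70 to 84 days.
   - 2 to 4 months: 61 to 122 days.
   - 2 to 6 months: 61 to 182 days.

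   Even counted from injection, a reading at day 56 to 66 comes before the end of every stated range. It can fall after the end of effect only near the shortest limit, by at most 66 − 61 = 5 days. Drug-related weakness would therefore often still be present. What one reading cannot show is when weakness began, how it ran before then, or an episode already over.

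5. **How much could be missed.** The documents give no event rate and no capture probability. Purely as an assumed range, let p be the true per-subject rate and c the chance that an event is recorded. With 10 subjects, expected recorded events are 10pc and P(none recorded) = (1 − pc)^10.

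| p (assumed) | c (assumed) | Expected recorded | P(none recorded) |
|---|---|---|---|
| 0.10 | 1.00 | 1.0 | 0.35 |
| 0.10 | 0.50 | 0.5 | 0.60 |
| 0.10 | 0.25 | 0.25 | 0.78 |
| 0.20 | 1.00 | 2.0 | 0.11 |
| 0.20 | 0.50 | 1.0 | 0.35 |
| 0.20 | 0.25 | 0.5 | 0.60 |

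The table shows how a small pilot responds to incomplete capture. It does not estimate what this trial will lose.

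**The case against.** The other side has real weight. Subjects are observed before discharge, and section 2.7.1 calls the main site reactions immediate, so that check is aimed at much of the second endpoint. Section 10.3 requires a prompted enquiry about the whole interval at the 2-month visit and already asks for onset and resolution times. Weakness is also measured objectively at that visit. Subjects know whom to call, and earlier follow-up is promised if weakness occurs. All of this stands. What remains is events that appear after discharge and pass before 2 months: the pre-discharge check precedes them, the earlier follow-up needs someone to report them, and the prompted enquiry depends on memory.

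A reader might infer four stronger points that the documents do not support:

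- *That neither endpoint is looked at until 2 months.* Sections 7 and 11.1.1 provide same-day observation.
- *That events will be under-counted, and by a known amount.* No capture rate is given, so only ‘may’ is justified.
- *That the 2-month reading misses weakness, or its worst point.* The stated durations mostly run past that visit, and no section says when weakness peaks.
- *That section 11.1 contradicts the calendar.* It says "the investigators will have regular follow up with the research participants to allow close monitoring for AE/SAEs". Contacts at 2, 4 and 6 months are regular, and whether they are close enough is a matter of judgement.

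**Conclusion.** The point holds as a gap in ascertainment. Apart from observation on the day, which has no recording step in Table 4, nothing is scheduled for about 8 to 9 weeks after injection, and the stated onset of effect lies inside that period. Site reactions confined to the gap, and the onset or short episodes of weakness, may be under-counted. The direction follows from the schedule; the size cannot be derived from the documents.

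This rests on two readings of the text: that Tables 3 and 4 and section 4.1 show every scheduled contact, and that the onset of about 2 weeks, which section 6.6 takes from other indications, applies here. It does not depend on which stated duration of effect is used. For an uncontrolled pilot of 10 subjects this is a worthwhile, inexpensive improvement.

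**What to change.** 1. In Table 4, add side-effect evaluation to study visit 1, so that the pre-discharge check is recorded, including when nothing is found.
2. In Tables 3 and 4, add one telephone call or REDCap survey at about 2 weeks after injection, with a fixed checklist: each site reaction in section 4.1.3 with start and end dates, leg weakness or tripping, and the distant-spread symptoms in section 2.7.1.
3. Use the same checklist at 2, 4 and 6 months, so that answers are comparable across contacts.

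Positive answers would go through the existing route in section 7.4.3; the change concerns data collection only.

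**Cost.** Ten short contacts (10 subjects × 1) and an amendment. Staff already plan 10 × 2 = 20 telephone follow-ups at 4 and 6 months, and REDCap is in use (section 9.2.2). The reported event rate will probably be higher.

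**Limit.** Weakness that starts after the 2-week contact would still depend on a call from the subject or on the 2-month visit, 42 to 52 days later. The change narrows the gap without closing it, and adds no strength measurement.
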